**Objectives:**

➤ **Primary objective :**

- To compare the online oral health education to the conventional oral health education regarding :
  1. Oral health knowledge of primary school children of 7-9 years old.
  2. Assessing oral hygiene measures practice in primary school children of 7-9 years old.

➤ **Secondary objective :**

Is to evaluate the efficacy of a new oral health education method to deliver health information to target population

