**Study hypothesis:****▪ Null hypothesis:**

No difference between the effectiveness of online oral health education and conventional oral health education methods on oral health knowledge and oral hygiene practice of primary school children

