### **Sample size calculation:**

Sample size estimation was based on testing the change in KAP before and after each educational intervention. The predicted sample size was found to be 265 children for each intervention, by assuming an  $\alpha$  level of 0.05,  $\beta$  level of 0.1 (power = 90%), allocation ratio of 1:1, to detect an effect size  $d$  of 0.2. After adding a 20% increase to adjust for dropout, the final sample size was 318 children for each intervention (total sample size = 636 children). Sample size calculation was performed using G\*Power software version 3.1.9.4 for MS Windows, Franz Faul, Kiel University, Germany.

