### **Study procedures:**

- 1) A literature review was conducted using electronic search engines like PubMed and Google scholar to identify studies assessing the effect of online and conventional oral health education on improving the oral health knowledge and practice in school children regarding their oral hygiene.
- 2) After reviewing many articles, a questionnaire was selected to assess the above outcomes. The questionnaire was chosen according to availability and effectiveness, and it was modified by simplifying and deselecting some of the questions that aren't related to the age group to better suit the age group of question.
- 3) A piloting session will be done on two separate classes, one from each educational stage to assess the modified questionnaire in terms of ease of understanding and comprehension to the participants. Those two classes will not be included in the final results of the study.
- 4) The questionnaire will be distributed before conducting the oral health education sessions (both online and conventional) to assess the pre-session knowledge and practice of the participants.
- 5) All questionnaires are self-administered but a well-trained interviewer will be available offering assistance in understanding the questionnaires if needed.
- 6) 3rd and 4th grade classrooms in each school will be randomly and evenly allocated to the interventions included in the study using computer-generated randomization application.
- 7) The researcher will be blinded of the classrooms of each school during the randomization process.
- 8) The researcher will be blinded of the names of the participants or their personal data during and after the questionnaire session.
- 9) After the questionnaire is finished, the researcher will then begin his educational lesson using electronic aids like a projector inside the classrooms or using Microsoft teams during the online session.
- 10) Another questionnaire will be distributed after the educational lesson for both session types to assess the post-session knowledge and practice in the participants.
- 11) A comparison will be carried out for the results of each question in both questionnaires and for the final results of both questionnaires to determine the statistical significance of both results.
- 12) These statistical results will be done by a separate statistician outside the study field and blinded from all the procedures.

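### The analysis described in the protocol compares pre-session with post-session questionnaires and names no online-versus-conventional contrast, although the objective and null hypothesis are between-arm

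*Protocol*

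**What the plan says.** The question is between-arm throughout. The primary objective (Protocol, Objectives) is "To compare the online oral health education to the conventional oral health education regarding" knowledge and practice. The null hypothesis (Study hypothesis) is "No difference between the effectiveness of online oral health education and conventional oral health education methods". The research question and aim say the same in other words.

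The analysis is described in Study procedures. Step 4 gives a questionnaire before the sessions, "to assess the pre-session knowledge and practice of the participants". Step 10 gives the second one: "Another questionnaire will be distributed after the educational lesson for both session types". Step 11 then opens at the level of single items: "A comparison will be carried out for the results of each question in both questionnaires". The same sentence goes on to the overall scores, with the comparison also to be made "for the final results of both questionnaires to determine the statistical significance of both results".

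The Sample size calculation section is based on "testing the change in KAP before and after each educational intervention", with an alpha of 0.05, a beta "level of 0.1 (power = 90%), allocation ratio of 1:1" and d = 0.2. It arrives at 265 per intervention, raised to 318 for dropout. Section 6, Statistical analysis, says who will analyse the data and when, but names no test or contrast.

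**The concern.** Read with steps 4 and 10, the two questionnaires in step 11 are the form before the lesson and the form after it. The comparison described is therefore a change over time, and the sample size section uses the same basis. Neither place names the contrast that the objective and null hypothesis require.

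A within-arm change is not evidence on the difference between methods. It mixes the effect of teaching with familiarity from having seen the form once already, and only the contrast between randomised groups removes that. If the only results are one before/after test per arm, a reader has nothing but two separate significance statements from which to judge the methods. One significant and one non-significant result can arise when the true gains are equal. Two significant results can arise when one method is clearly better.

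**Working it through.** **1. Reproducing the plan's figure.** Inputs from Sample size calculation: alpha 0.05 (sidedness not stated), power 90%, d = 0.2. For a paired t-test the noncentrality is d√n with n − 1 degrees of freedom. At n = 265 it is 0.2 × √265 = 3.256, and exact two-sided power is 0.9004; at n = 264 it is 0.8993. So 265 is the smallest n that reaches 90%. The alternatives do not give 265:

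| Test of d = 0.2, 90% power | n |
|---|---|
| Paired, two-sided | 265 |
| Paired, one-sided | 216 |
| Two-sample, two-sided | 527 per arm |
| Two-sample, one-sided | 429 per arm |

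The dropout step is 265 × 1.2 = 318. The sizing is therefore a within-arm paired test, which supports reading step 11 as pre versus post.

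**2. Equal true gains: how often do two within-arm tests disagree?** With p the power in each arm, exactly one arm is significant with probability 2p(1 − p). Gains are in SDs of the change score and are assumed, because the protocol gives none. There are 265 children per arm, treated as independent.

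| Gain in both arms | p | 2p(1 − p) |
|---|---|---|
| 0.10 | 0.368 | 46.5% |
| 0.12 | 0.495 | 50.0% (the maximum, reached at p = 0.5) |
| 0.15 | 0.682 | 43.4% |
| 0.20 | 0.900 | 17.9% |
| 0.25 | 0.982 | 3.6% |
| 0.30 | 0.998 | 0.4% |

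**3. Unequal true gains: how often do both tests come out significant?** This is the product of the two powers. For gains of 0.3 and 0.6 SD it is 99.8%. A direct two-sample test of the 0.3 SD gap has noncentrality 0.3 × √(265/2) = 3.453 and power 93%. For gains of 0.3 and 0.5 SD, both are again significant in 99.8% of trials, and the direct test has 63% power.

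**4. Power of the test that the hypothesis needs.** For a between-arm d = 0.2, the noncentrality with 265 per arm is 0.2 × √(265/2) = 2.302 and power is 63%. With 318 per arm it is 0.2 × √(318/2) = 2.522 and power is 71%. The difference detectable at 90% power with 265 per arm is (1.960 + 1.282) × √(2/265) = 0.28.

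Two things move these figures. Adjusting for the pre-session score rather than analysing raw change multiplies the variance by (1 + r)/2, which is 0.65, 0.75 and 0.85 at assumed pre/post correlations of 0.3, 0.5 and 0.7. Allocation by classroom works the other way. The protocol gives neither a correlation nor an intraclass correlation.

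**The case against.** Step 11 is one loosely worded line in a list of procedures, not an analysis plan. Its closing phrase about both results has no clear referent and may be meant to cover the two session types. Section 6 leaves the methods to a statistician, a statistical analysis plan may exist, and anyone given this protocol would have a between-method hypothesis in front of them. Much of this stands. A reader might infer that the trial will never test online against conventional, or that randomisation goes unused. The documents do not support that: step 6 randomises classrooms, and nothing in step 11 rules out a contrast by allocation.

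A reader might also infer that two within-arm p-values will be set side by side and read as difference or equality. No section says so; that is a risk of the wording, not a stated rule. The scenarios are chosen as well. The 50% figure is the worst case. If gains are large, as may be expected from a lesson followed at once by a questionnaire, a false difference becomes rare and the missed difference is the main risk.

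The objection does not dispose of the mismatch. The point is not that a test has been left to a later document. The protocol states a comparison and sizes the trial for it, and that comparison is not the one in its own null hypothesis. Even if the closing phrase does cover both session types, testing each for significance is not testing their difference.

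**Conclusion.** The point holds in this form: the analysis described, and the sample size built on it, are within-arm and name no between-arm contrast, while the primary objective and null hypothesis are between-arm. Followed as written, the analysis does not test the trial's hypothesis. The reproduction of 265 needs no assumption beyond a two-sided test.

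The error rates only illustrate why inference from separate tests would be unreliable. They rest on assumed gains, 265 per arm and independent children. The stated 90% power belongs to the within-arm test only; the figure of about 63% for the between-arm test takes d = 0.2 as the difference between methods and precedes any loss to clustering. The sizing matter has the same root and should not be counted as a second, independent fault.

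**What to change.** Rewrite step 11 so that the primary analysis is one between-arm comparison, online minus conventional, of the final post-session questionnaire score. Adjust it for the pre-session score and school, allow for allocation by classroom, and report the difference with a 95% confidence interval. Keep within-arm changes as description, and draw no conclusion about the methods from them. A between-arm test of change or of unadjusted post-session scores would also address the hypothesis; baseline adjustment is preferred because the pre-session score is already collected and the adjustment reduces variance.

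The change is mainly wording and needs no new measurement, but it has costs to state:

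- **Linked forms.** Each child's pre and post forms must be joined. Step 8 keeps names from the researcher and Ethical consideration promises anonymity, but no linking code is described. An anonymous study code would do this; the paired sample-size calculation already presumes such linkage.
- **Power statement.** Restate it for the between-arm test: about 63% with 265 per arm and 71% with 318 for d = 0.2, before clustering, with the assumed correlation and intraclass correlation shown. Restating the power is the remedy proposed here, not increasing enrolment.
- **Time point.** The PICOTS framing mentions follow-up every three months, so the new step should say which post-session questionnaire is primary.

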**Ethical consideration:**

All participants' parents will be briefed about the nature of the study and an **informed consent form** will be delivered to them both in Arabic and English languages for their approval to include their children's data in the study. This informed consent will be available and approved by the Ethical Committee of Faculty of Dentistry, Ain Shams University. There will also be an assent from each child to freely accept or decline joining the study prior to the questionnaire. Parents and/or children will be given the complete freedom to complete or quit the study whenever they want. Also, they will be assured of the confidentiality of their personal information and anonymity. The participants who won't participate in the study or are excluded will receive the oral health education in both methods (online and conventional) nonetheless as it is ethically not appropriate for one person to receive the health education service while the other doesn't in the same working / studying space.

**5. Data management:**

Data for each classroom will be collected through laptops (Google forms) or printed questionnaires, according to the nature of the session delivered. Results will be monitored and inserted into an excel sheet.

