**NCT number: NCT05570500**

**Date of document: November 21st, 2020**

## **1. Background:**

Caries is one of the greatest challenges facing the health system in Egypt, and as of the past few years studies have shown that Egyptian children have many dental problems, including: untreated dental caries, forms of periodontal diseases and even irregular tooth brushing habits. The latter being mainly due to the ignorance of children of understanding the correct technique of tooth brushing, which may have been due to the lack of dental awareness that these children receive, either by dental professionals who should offer this service regularly [1] or due to poor parental awareness of the factors that affect the oral health status of their children [2].

Oral health (OH) education has proven to play a significant role in improving the knowledge, attitude and behaviour of children [3]. Implementing Oral health education in schools tend to improve the children's OH-related quality of life because engaging children at younger age regarding their habits, practices or knowledge tends to stay with them till adolescence then to adulthood [4].

In the year 2019 the Covid crisis has globally struck, being recognised by the WHO as a pandemic on March 11th, 2020 [5] the world was set in motion for various changes in the daily life of every man, woman and child. Covid 19, as defined by the WHO, is an infectious disease that spreads through droplets of saliva or discharge from the nose when the infected person sneezes or coughs, and thus the best way to avoid being infected by this disease is through some precautions that include social distancing of at least 1-2 meters between each person [6]. In Egypt, 75% of school children are usually very crowded in classrooms, which sometimes might reach 40 students per classroom or even more in certain schools [7]. Such numbers pose a great challenge to fulfilling the Covid precautions set by the WHO.

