Luckily, we are in an era of technological advancement and the need for the electronic communication has risen to its peak. Recently, Egyptian ministry of education had applied the online education system as a must have in all schools and even released an online governmental portal which provides E-learning service, which in turn, would allow the students to remain at home while receiving their education [8]. Oral health education, which is considered as a part of the health promoting schools according to the WHO [9], has been known to be effective at

direct contact between the educator and the recipients [10], and many modifications in the way of delivering knowledge to children has been improved to include games, drama scenes and flash cards [11]. The challenge nowadays is that with the Covid outbreak the need for more distancing and less direct contact between people has increased, and the conventional methods of health education might deem unfit towards the global direction to control the Covid outbreak.

The online methods of delivering oral health education has been shown to be effective using Motivational Interviewing (MI) [12]. MI, defined by Miller & Rollnick (2002) as a technique based on evidence, centred on the individual, and individually-tailored. This technique is meant to prepare the participant for change by motivating and promoting the participant's solutions to the inconsistency of decisions towards self-improvement [13]. Few studies have engaged young adolescents through MI [14], yet with young children the MI results are still under investigation [15]. With the Covid outbreak still on the loose, oral health educators must follow the guidelines presented by the WHO to prevent its spreading all the while providing oral health education service to school children. Hence finding ways to implement the oral health education into the online education system is challenging yet an important step to address young children in these hard times, in order to help them understand how to take care of their oral hygiene while keeping them, their families and their environment safe from harm.

2. **Research question:** is the online method of delivering oral health knowledge to primary school children is as effective as the conventional methods regarding their knowledge and practice towards personal oral hygiene?

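### Questionnaire mode (Google Forms or paper) is set by session type, which is the randomised arm, so any mode effect is confounded with teaching method

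*Protocol*

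**What the plan says.** Section 5 (Data management) fixes the mode of data collection: "Data for each classroom will be collected through laptops (Google forms) or printed questionnaires, according to the nature of the session delivered". 

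In Study procedures, step 6 has "classrooms in each school will be randomly and evenly allocated to the interventions included in the study". Step 9 describes the two kinds of session: "using electronic aids like a projector inside the classrooms or using Microsoft teams during the online session". Steps 4 and 10 give a questionnaire before and after the lesson in both kinds of session. Step 5 makes every questionnaire self-administered, with a trained interviewer on hand. Step 11 describes the analysis: "A comparison will be carried out for the results of each question in both questionnaires and for the final results of both questionnaires".

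The primary objective is "To compare the online oral health education to the conventional oral health education regarding" knowledge and practice. The sample size rests on "testing the change in KAP before and after each educational intervention".

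No section sets a mode common to both arms. The pilot in step 3 tests whether children understand the questionnaire, not whether paper and screen give the same answers.

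**The concern.** The questionnaire is the only outcome instrument described, and children aged 7 to 9 complete it themselves. If they answer differently on a screen than on paper, the between-arm difference is the teaching effect plus whatever part of the mode effect the analysis does not remove.

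Because mode follows arm at every assessment, the data contain no paper children taught online and no screen children taught conventionally. A later analysis plan can choose a contrast in which a constant shift drops out. It cannot estimate or remove a mode effect that changes between the two questionnaires. The rule therefore has to be settled before data are collected.

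**Working it through.** **Step 1. Does mode follow arm?** Section 5 ties mode to session type. Study procedures steps 6 and 9 make session type the randomised allocation. The protocol does not spell out which session gets which mode, but either mapping aligns mode with arm.

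**Step 2. The plan's own figure.** A paired t-test with d = 0.2, two-sided alpha 0.05 and power 0.90 gives n = 265 (power 0.9004), matching the protocol. 265 × 1.20 = 318, and 2 × 318 = 636. The sample size is thus a within-arm pre-post calculation. It does not define the between-arm contrast.

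**Step 3. What survives in each contrast.** Let the mode shift between arms be b_pre and b_post, in SD units, and let rho be the pre-post correlation. The bias in the between-arm difference is:

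- Change score: b_post − b_pre. This is zero for a constant shift.
- Baseline-adjusted: b_post − rho × b_pre. For a constant shift b this is b(1 − rho).
- Post-only: b_post, with nothing removed.

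**Step 4. Illustrative size.** From the protocol: 265 per arm and alpha 0.05. Assumed: shift size, intraclass correlation (ICC), rho, and class size m. The value m = 40 borrows the Background remark that Egyptian classes "sometimes might reach 40 students per classroom or even more in certain schools", which is not a figure for these two schools. Classrooms are randomised, so clustering is allowed for:

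- Design effect DE = 1 + (m − 1) × ICC; effective n = 265/DE; df = 2 × (265/m) − 2.
- False-positive rate from a noncentral t with noncentrality b × sqrt(effective n / 2) and no true difference.

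For m = 40 and ICC 0.05: DE = 1 + 39 × 0.05 = 2.95, effective n = 265/2.95 = 89.8, df = 2 × 6.625 − 2 = 11.25.

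| m | ICC | DE | b = 0.05 | b = 0.10 | b = 0.20 |
|---|---|---|---|---|---|
| 40 | 0.05 | 2.95 | 6.1% | 9.4% | 23.3% |
| 40 | 0.02 | 1.78 | 6.8% | 12.4% | 35.2% |
| 40 | 0.10 | 4.90 | 5.7% | 7.6% | 15.9% |
| 20 | 0.05 | 1.95 | 6.8% | 12.4% | 35.4% |

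Here b is the part that does not cancel, in SDs of the score compared.

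**Step 5. A constant shift of 0.20 SD (m = 40, ICC 0.05).**

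- Change score: bias 0, false-positive rate 5%.
- Baseline-adjusted: bias 0.20(1 − rho) = 0.14, 0.10, 0.06 for rho = 0.3, 0.5, 0.7. Divided by the residual SD, sqrt(1 − rho²), this is 0.147, 0.115, 0.084, giving 14.7%, 10.9% and 8.1%.
- Post-only: 23.3%.

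**Step 6. Can the baseline reveal the shift?** The pre-session between-arm difference has SE = sqrt(2 × 2.95/265) = 0.149 SD. With t = 2.195 on 11.25 df, the 95% half-width is 0.33 SD (0.25 at ICC 0.02, 0.42 at ICC 0.10). That cannot rule out a shift of 0.2 SD, and it says nothing about a shift that appears only after teaching.

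**Step 7. The price of relying on change scores.** In units of the score variance, a change score has variance 2(1 − rho) and a baseline-adjusted score 1 − rho². The ratio is 2/(1 + rho) = 1.54, 1.33, 1.18 at rho = 0.3, 0.5, 0.7, or about 54%, 33% and 18% more variance.

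**The case against.** The strongest reply is that the harm is conditional. The only quantity the protocol sizes is pre-to-post change. The two questionnaires of step 11 most naturally mean the pre- and post-session ones. Section 5 sets mode per classroom, so a constant shift would drop out of change scores. Nothing in the protocol suggests that a mode effect differs before and after a lesson. Both arms also self-complete with help available, so the stated contrast is paper against screen, not self-report against interview.

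Most of this stands, and it limits the point. It does not remove it. The protocol implies but does not say that each classroom keeps its mode. The sample-size basis is within-arm, and step 11 does not name the between-arm contrast. Baseline adjustment leaves part of even a constant shift.

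Two stronger readings are tempting. A reader might infer that the between-arm result is bound to be biased, or that the false-positive rates above are forecasts. The protocol supports neither: it gives no size or direction for a mode effect, and every shift used here is assumed. A reader might also infer that the protocol plans a comparison of post-session scores alone. No section specifies one.

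**Conclusion.** The point holds in a limited form. The alignment of mode with arm follows from the protocol's wording and needs no assumption. Its consequence depends on the contrast and on a mode effect of unknown size. A constant shift does no harm in change scores if mode is fixed within classroom, leaves a fraction 1 − rho under baseline adjustment, and passes in full into a post-only comparison. A shift that differs from pre to post biases all three.

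Under the assumptions in the working, an uncancelled shift of 0.20 SD takes a 5% false-positive rate to between 16% and 35%; a shift of 0.05 SD barely moves it (about 6% to 7%). These figures show sensitivity and are not the reason to act. The reason is that the confounding is easily avoided beforehand and cannot be fully undone afterwards. It should be corrected.

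**What to change.** Change section 5 so that both arms complete the questionnaire in one common mode before and after the lesson, and at any follow-up where it is repeated. (PICOTS gives three-monthly follow-up, but no section says how those data are collected.) Google Forms for all or paper for all would serve, whichever the schools can support. The same physical setting is not needed.

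Both modes are already planned, so no new instrument or sample size is required. The cost is laptops at questionnaire time for the conventional classes (up to 318 children) or printed forms for the online classes. The protocol states neither device availability nor where online children sit. If they are at home, as the Background describes for online schooling ("would allow the students to remain at home while receiving their education"), paper just before and after a lesson would be hard to hand out and collect, and Google Forms for all would be more workable.

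If one mode is not feasible, state in section 5 that each classroom keeps the same mode from pre to post, and report that mode is confounded with arm. A change-score comparison can be added as a sensitivity analysis, since it removes a constant shift. It should not be mandated as primary, because that would trade the precision shown in step 7 against a bias of unknown size.
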